## 2 PROTOCOL SYNOPSIS

Title	Phase I/II clinical trial of Daratumumab in patients with relapsed acute myeloid leukemia post-allogeneic hematopoietic stem cell transplant.
Protocol Short Title	Daratumumab in post-transplant relapse
Name of Drug	Daratumumab
Study Rationale	

1. IFN-<math>\gamma</math> promotes graft-versus-leukemia effects without directly interacting with leukemia cells in mice after allogeneic hematopoietic cell transplantation.

2. Endogenous IFN-gamma levels are elevated in post-transplant patients post-conditioning, infections, GVHD, and during hematopoietic regeneration.

3. We hypothesize that (i) IFN-gamma levels will be higher in post-transplant patients than healthy donors (ii) combination of Daratumumab and endogenous IFN-gamma will mediate antileukemic efficacy post-transplant (iii) the combination of Dara and donor lymphocytes will provide potent effectors, recruit effectors to marrow and mediate GVL.

Treatment Duration	8 weeks; Daratumumab may be continued beyond 8 weeks if clinical benefit is observed up to 12 months.
Dosing Schedule	Weekly Dara for 8 doses
Route	Intravenous
Age range	$\geq 18$ years
Study Duration	10 months to 3.5 years for phase I; 24 months for phase II.
Sample size	8-40 patients for Phase I; 25 patients for phase II
Inclusion Criteria	

1. Patients <math>\geq 18</math> years

2. AML relapse following Allo-HSCT (Morphological relapse, or MRD positive verified by flow cytometry, cytogenetics, and molecular mutations)

Date of protocol: 10/14/2020

IRB Approval Date: 11/24/2020

Version of protocol: 7

IND number: 139015

Institutional protocol number: OSU 17102

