Date of protocol: 10/14/2020

IRB Approval Date: 11/24/2020

Version of protocol: 7

IND number: 139015

Institutional protocol number: OSU 17102

DLT definition	

• Acute GVHD <math>\geq</math> Grade 3

• Any non-hematologic toxicity <math>\geq</math> Grade 3 related to Daratumumab

• Hematologic toxicity: grade 4 toxicity not related to the underlying disease and not responding to growth factor or transfusion within 7 days

• Grade 3 or higher non-neurologic immune-related adverse events (e.g. diarrhea, pruritus, rash) that responds to corticosteroids and improve to grade 1 or less within 4 weeks will NOT count as DLTs. Optional biopsy of affected organs will be encouraged to help determine whether the immune-related condition is due to GVHD

Enrollment schedule	
Dose level 1: Weekly Dara for eight doses; if no infusional toxicity observed or GVHD observed, proceed to next dose level. 3 patients at a time can be enrolled in one dose level.
 
If no GVHD is observed after at least 2 weeks after DLI, enrollment will proceed to next dose level.

Definitions for safety-evaluability	Received at least one dose of Daratumumab
Definition for DLT evaluability	
All patients are evaluable for DLT except patients who are unable to receive 3 doses of daratumumab in dose level 1, or 3 doses of daratumumab and DLT for dose levels 2 and 3 due to progression of AML.
 
DLT observation period will be from the first dose of daratumumab till 7 days post 3rd dose of daratumumab (for dose level 1) and from the first dose of daratumumab till at least 4 weeks post DLI (for dose level 2 and 3)

Definitions for efficacy evaluability:	All eligible patients who receive at least one dose of Daratumumab, do not withdraw consent, and are evaluated for response at week 8.
Dose-limiting toxicity:	Grade 3 or 4 GVHD
Special situations	

1. If patients attain response before DLI, there will be three options at the discretion of treating physician :

a. Proceed with DLI

Date of protocol: 10/14/2020

IRB Approval Date: 11/24/2020

Version of protocol: 7

IND number: 139015

Institutional protocol number: OSU 17102

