## 7.2 NUMBER OF PATIENTS

For phase I, we expect to enroll a minimum of 3 and a maximum of 18 patients for the related donor portion and 3-18 patients for the unrelated donor cohort. Accounting for 10% unevaluable for DLT, we expect 4-20 patients for each cohort in summary we expect 8-40 patients for phase I portion of the study. Enrollment can occur in parallel for both related and unrelated donor arms of the study. For Phase II, we will expect to enroll 25 patients.

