If a patient in dose level 1 receives less than 3 doses of Daratumumab due to reasons other than toxicity, then this patient will not be evaluable for DLT and will be replaced. An additional patient will be added to the dose cohort. For dose level 2 or 3, if a patient does not receive 3 doses of Daratumumab and DLI due to reasons other than toxicity, then this patient will not be evaluable and will be replaced. There will be no intrapatient dose escalation. Phase I may involve as few as 3 patients (three at the starting dose level if  $\geq 2$  DLTs are experienced) and a maximum of 18 patients will be treated, six at each of the 3 dose levels. We assume that 10% of the patients in this group will not be evaluable due to not finishing the DLT observation period. So we expect to accrue a minimum of 4 patients and a maximum of 20 patients.

At OSU, 125 patients with AML/MDS underwent allo-HSCT in 2012 and 2013. Among these, 32 patients relapsed. About 40% were from related donor and 60% from unrelated donor. So we expect to accrue approximately 6 patients for the related sibling donor cohort and 10 patients for the unrelated donor cohort per year. Hence, the minimum study duration for phase I would be about 8-10 months and the maximum study duration would be around 2.5-3.5 years (accounting for the DLT observation period) for related sibling donors and unrelated donors respectively.

After the MTD has been established, we will expand to Phase II trial. For phase II part, considering that patients receiving transplant from related sibling donor or unrelated donor with each treated at the corresponding MTD of Daratumumab plus DLI are expected to have similar profiles for response and toxicities, we will combine these 2 cohorts together in phase II stage. The null hypothesis is that combination of Daratumumab and DLI has a response rate of < 10% in patients with relapsed AML following allo-HSCT. The alternative hypothesis is that Daratumumab has a response rate of at least 30% in patients with relapsed AML following allo-HSCT. With a type 1 error (alpha): 0.05, and a type 2 error (beta = 1 – power): 0.20, the sample size would be 25 patients for Phase II. If the number of patients achieving ORR is 6 or more, then we reject the null hypothesis. We would include 3-6 patients from

Date of protocol: 10/14/2020

IRB Approval Date: 11/24/2020

Version of protocol: 7

IND number: 139015

Institutional protocol number: OSU 17102

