phase I who are treated at MTD in phase II analysis. Assuming 10% of the patients would be not evaluable for efficacy, we would expect to enroll 25 patients in phase II. With approximately 16 patients per year, and the study duration for phase II would be around 2 years including the follow up period (6-months).

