### 16.2 Analysis methods:

Analysis datasets:

Efficacy sets: All evaluable patients will be included in the analysis of the primary endpoint. The term evaluable is defined as any eligible patient who receives at least one dose of Daratumumab, does not withdraw consent, and is evaluated for response week 8; patients who fail to have a week-8 assessment due to early progression, death or toxicity will also be considered evaluable for response and categorized as non-responders. Patients who fail to have a week-8 assessment for other reasons (e.g., refusal due to travel constraints) will be considered unevaluable and will not be included in the denominator when calculating ORR rate.

Safety sets: The safety analysis dataset will include all eligible patients who receive one dose of daratumumab.

The adverse events will be examined and worst grade adverse events will be recorded for each patient and summarized by type, severity, and attribution (if possible) using NCI CTCAE version 4 criteria. Tolerability of the regimen will be assessed by summarizing the number of patients who require dose modifications and/or dose delays. In addition, we will also capture the proportion of patients who go off treatment due to adverse events or even those who refuse further treatment for lesser toxicities that inhibit their willingness to continue participation on the trial. All patients who have received at least one dose of daratumumab will be evaluable for toxicity and tolerability.

The primary endpoint of phase II is to evaluate overall response rates (ORR) to the combination of Daratumumab and DLI. The ORR will be defined as complete remission (CR), complete remission with incomplete marrow recovery (CRi), partial remission (PR) and morphological leukemia free

Date of protocol: 10/14/2020

IRB Approval Date: 11/24/2020

Version of protocol: 7

IND number: 139015

Institutional protocol number: OSU 17102

state (MLFS). The proportion of patients achieving ORR among efficacy sets will be calculated and 95% confidence interval will be estimated. In addition, the ORR among patients who received at least 3 doses of Daratumumab and DLI will be calculated as well. The ORR rate among MRD positive patients and patients with overt morphological relapse will be estimated as well. The MRD conversion rate from MRD positive to MRD negative, and the 3-month GVHD rate (both grade II-IV and III-IV) will be similarly analyzed.

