Demographical and clinical characteristics of study patients will be described using mean and standard deviation, median and range, or frequency and percent depending on the data type and distribution. Overall survival (OS) will be defined as the time from the first treatment of Daratumumab to death or last contact date if no death. Progression free survival (PFS) will be defined as the time from the first treatment of Daratumumab to the date of progression or death or last clinical assessment date if no progression or death. Kaplan-Meier curves will be generated to estimate OS/PFS at 6 months. The association between patient characteristics and OS/PFS will be evaluated in univariable Cox proportional hazard regression model.

To examine the rate of GVHD (both grade II-IV and III-IV), the event will be onset of GVHD and time to GVHD will be defined as the period of time from first treatment of Daratumumab to the onset of GVHD. Death and early relapse without GVHD will be competing risks. Cumulative incidence rate of GVHD at 3-month with 95% confidence intervals will be estimated from the cumulative incidence curves. Competing risk regression analysis will be conducted to estimate the association between patient characteristics and GVHD.

For pre/post-treatment comparisons in the correlative part of the study, a paired t-test will be applied. Two-tailed p values <0.05 will be considered statistically significant in all analyses.

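### The phase II rule of six or more responders keeps alpha at 5% and power at 80% only if 25 to 27 patients are analysed, and the plan does not fix that number

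*Combined protocol and SAP*

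**What the plan says.** Section 16 tests a null response rate below 10% against an alternative of at least 30%, with alpha 0.05 and beta 0.20, and arrives at 25 patients. The decision rule follows: "If the number of patients achieving ORR is 6 or more, then we reject the null hypothesis". No denominator is attached to the six.

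The next sentences alter the number analysed:

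- Phase I patients treated at the MTD enter the phase II analysis: "We would include 3-6 patients from" phase I.
- Losses are allowed for, yet the enrolment figure equals the calculated sample size: "Assuming 10% of the patients would be not evaluable for efficacy, we would expect to enroll 25 patients in phase II".
- Section 16.2 limits the primary analysis to evaluable patients. Those who miss week 8 because of early progression, death or toxicity count as non-responders. Those who miss it for other reasons "will be considered unevaluable and will not be included in the denominator when calculating ORR rate".

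The synopsis ("8-40 patients for Phase I; 25 patients for phase II") and section 7.2 ("For Phase II, we will expect to enroll 25 patients") count enrolment in the two phases separately.

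Two other statements bear on the same test. The synopsis defines efficacy evaluability as "All eligible patients who receive at least one dose of Daratumumab, do not withdraw consent, and are evaluated for response at week 8", without the provision for early failures found in section 16.2. Section 16.2 also says: "Two-tailed p values <0.05 will be considered statistically significant in all analyses".

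**The concern.** A fixed number of responders controls the error rates only for the sample size it was derived for. With more patients analysed, six responses become easier to reach by chance and the false-positive rate rises. With fewer, power falls. The plan leaves four things open: whether the 3-6 phase I patients sit inside the 25 or on top of it, whether 3-6 is a total or a figure for each donor cohort, whether unevaluable patients are replaced, and what cut-off applies if the analysed number is not 25.

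This rule decides the only primary efficacy test in phase II. The trial is open and single-arm, and responses of the phase I patients at the MTD will be known before phase II is analysed. A choice of denominator or cut-off made at that stage would be made with part of the outcome in view.

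**Working it through.** **Inputs.** From section 16: null rate 0.10, alternative 0.30, alpha 0.05, power 0.80, n = 25, cut-off 6, 3-6 phase I patients included, 10% unevaluable, 25 enrolled.

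**Formula.** With X ~ Binomial(n, p), alpha = P(X ≥ 6 | n, 0.10) and power = P(X ≥ 6 | n, 0.30).

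**The plan's own figure.** At n = 25, alpha = 0.0334 and power = 0.8065. A search for the smallest n with exact one-sided alpha at most 0.05 and power at least 0.80 returns n = 25 with cut-off 6. The stated design therefore reproduces as a one-sided exact test. An exact test with 0.025 in the upper tail would instead give n = 29 with cut-off 7.

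**The same cut-off at other n:**

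| n analysed | alpha | power | both targets met |
|---|---|---|---|
| 22 | 0.018 | 68.7% | no (power) |
| 23 | 0.023 | 73.1% | no (power) |
| 24 | 0.028 | 77.1% | no (power) |
| 25 | 0.033 | 80.7% | yes |
| 26 | 0.040 | 83.7% | yes |
| 27 | 0.047 | 86.4% | yes |
| 28 | 0.055 | 88.7% | no (alpha) |
| 29 | 0.064 | 90.7% | no (alpha) |
| 30 | 0.073 | 92.3% | no (alpha) |
| 31 | 0.083 | 93.7% | no (alpha) |

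**The n implied by each reading:**

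1. Phase I patients within the 25, 10% lost: 25 × 0.9 = 22.5, so 22-23 analysed. Alpha is 1.8-2.3% and power 69-73%.
2. Phase I patients added, 10% lost overall: 28 × 0.9 = 25.2 and 31 × 0.9 = 27.9, so about 25-28 analysed. Alpha is 3.3-5.5%.
3. Phase I patients added, loss applied only to the 25 new patients: 22 + 3 = 25 up to 23 + 6 = 29. Alpha is 3.3-6.4%.
4. Phase I patients added, none lost: 25 + 3 = 28 to 25 + 6 = 31. Alpha is 5.5-8.3%.
5. Phase I patients added, with 3-6 taken as per cohort in two cohorts (an assumption): 25 + 6 = 31 to 25 + 12 = 37 with none lost, alpha 8.3-16.0%. With 10% lost, 31 × 0.9 = 27.9 and 37 × 0.9 = 33.3, so about 28-33, alpha 5.5-10.6%.

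**Sidedness.** If the two-tailed statement governed the primary test, the upper tail would have to be at most 0.025. With a cut-off of 6 that requires n ≤ 23, where power is at most 73.1%. No n would then meet both targets.

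**Smallest cut-off with exact one-sided alpha at most 0.05:** 6 for n = 21-27, 7 for n = 28-34, 8 for n = 35-41. Power at 30% with that cut-off is 78.0% at n = 28, 81.2% at 29, 84.1% at 30, 86.5% at 31 and 86.7% at 35.

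**The case against.** The design calculation is right, and there is a reading under which the paragraph is coherent. If 3 of the 25 analysed patients come from phase I, 22 new evaluable patients are needed; 22 / 0.9 = 24.4, which rounds up to 25 enrolled. That explains why 25 appears twice, fits the separate enrolment counts in the synopsis and section 7.2, and keeps the analysed number at 25. On this view the gap is one of clarity. The larger alpha values need either no losses, against the plan's own 10% assumption, or a per-cohort reading that the text does not state. The 69-73% power figure needs a loss allowance that never raised enrolment.

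Much of this is fair. The calculation at n = 25 is not in error, the per-cohort figures are conditional, and on the most natural reading the excess in alpha is modest. But the plan does not write that reading down, and it holds only near the low end of the plan's own 3-6 range. With 22-23 evaluable new patients and 6 from phase I, 28-29 are analysed and alpha is 5.5-6.4%. The per-cohort reading has some support too, since section 16 escalates the donor cohorts separately and gives each its own MTD.

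The two-tailed sentence and the synopsis definition could be treated as separate points. They belong here because each changes the threshold or the denominator of this same test.

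**Conclusion.** The concern holds. With a cut-off of six, both stated error rates are met only at 25, 26 or 27 patients analysed, and the plan's own provisions allow numbers on either side of that band.

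If the phase I patients are added, the rule works with 3 added and 10% lost. It exceeds 5% at the upper end: 5.5% at n = 28, 6.4% at n = 29, and 8.3% at n = 31 with no losses. If they are within the 25, alpha is safe but power drops to 69-73% after 10% loss. Alpha up to 16.0% arises only if 3-6 is per cohort and nobody is lost.

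These figures rest on an exact one-sided binomial test, which returns the plan's own n and cut-off, and on the stated rates of 10% and 30%. The separate enrolment counts favour the added reading but do not settle it. This should be fixed before phase II is analysed.

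**What to change.** In section 16:

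- State whether the 3-6 phase I patients are within the 25 or added to it, whether 3-6 is a total or per donor cohort, and whether unevaluable patients are replaced.
- Replace the fixed count with an exact one-sided 5% binomial rule at the number analysed: reject at 6 or more for n = 21-27, 7 or more for n = 28-34, 8 or more for n = 35-41.
- Restate power at the expected n.
- Say that the primary test is one-sided and exempt it from the general two-tailed statement in section 16.2.

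In the synopsis, bring the efficacy evaluability definition into line with section 16.2, so that early progression, death or toxicity before week 8 counts as non-response in both places.

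Fixing the primary analysis at exactly 25 evaluable patients, with a stated rule for how phase I patients count and for replacement, would also work. It would still need a cut-off for the case where 25 is not reached or is exceeded.

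The cost is a few lines in section 16 and one in the synopsis. No extra patients are needed to control alpha. The price is power at some n: 78.0% at n = 28 with cut-off 7, and, as under the current rule, 77.1% at n = 24 and 68.7% at n = 22 with cut-off 6. Power is at least 80% at n = 25-27 and at every n from 29 to 41.

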	

8. Patients must not have chronic obstructive pulmonary disease with a forced expiratory volume in 1 second (FEV1) < 50% of predicted normal. FEV1 is required for patients suspected of having chronic obstructive pulmonary disease and are not eligible if FEV1 is < 50% of predicted normal.

9. Patients must not have moderate or severe persistent asthma within the past 2 years and must not have currently uncontrolled asthma of any classification.

10. History of grade IV anaphylactic reaction to monoclonal antibody therapy

11. Active autoimmune disease prior to transplant

12. Pregnancy

13. Female patients of childbearing potential who are sexually active and unwilling to use an effective barrier method of birth control to avoid pregnancy during the study and for a minimum of 3 months after study treatment

14. Male patients who wish to donate sperm or with partners of childbearing potential who are sexually active and unwilling to use an effective barrier method of birth control to avoid pregnancy during the study and for a minimum of 3 months after study treatment

15. Concurrent use of any other investigational drugs

Study Design	

1. Phase I study (3+3 study design) with the following dose levels: For related sibling donors:

a. Dose level 1: Dara 16mg/kg

b. Dose level 2: Dara 16mg/kg + DLI at weeks 3-5: 1x10e6 CD3/kg

c. Dose level 3: Dara 16mg/kg + DLI at weeks 3-5: 1x10e7 CD3/kg

 For unrelated donors:

Date of protocol: 10/14/2020

IRB Approval Date: 11/24/2020

Version of protocol: 7

IND number: 139015

Institutional protocol number: OSU 17102

	

d. Dose level 1: Dara 16mg/kg

e. Dose level 2: Dara 16mg/kg + DLI at weeks 3-5: 1x10e5 CD3/kg

f. Dose level 3: Dara 16mg/kg + DLI at weeks 3-5: 1x10e6 CD3/kg

 
For haploidentical donors:
 

g. Dose level 1: Dara 16mg/kg

h. Dose level 2: Dara 16mg/kg + DLI at weeks 3-5: 1x10e4 CD3/kg

i. Dose level 3: Dara 16mg/kg + DLI at weeks 3-5: 1x10e5 CD3/kg

 
2. Phase II study with maximal tolerated dose as established for both related and unrelated donors. The MTD for the DLI may be different for related and unrelated donors.

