## 16 STATISTICAL CONSIDERATIONS

Study design/Sample size

This is a phase I/II study evaluating the combination of Daratumumab and escalating doses of DLI in patients with relapsed AML or transformed from MDS to AML post allo-HCT. Three dose levels will be used for related sibling donors and unrelated donors respectively.

Study Design: The standard 3+3 design will be applied to determine MTD of donor lymphocyte infusion when given with a fixed dose of Daratumumab. The dose escalation process for related sibling donor and unrelated donor will be conducted concurrently, but separately.

Dose escalation will proceed within each cohort according to the following scheme.

Number of Subjects with DLT at a Given Dose Level	Escalation Decision Rule
0 out of 3	Enter 3 subjects at the next dose level.
1 out of 3	
Enter 3 more subjects at this dose level.
 

• If 0 of these 3 subjects experience DLT, proceed to the next dose level.

• If 1 or more of this group suffer DLT, then dose escalation is stopped, and this dose is declared the maximally administered dose. Three (3)

Date of protocol: 10/14/2020

IRB Approval Date: 11/24/2020

Version of protocol: 7

IND number: 139015

Institutional protocol number: OSU 17102

	additional subjects will be entered at the next lowest dose level if only 3 subjects were treated previously at that dose.
>2	Dose escalation will be stopped. This dose level will be declared the maximally administered dose (highest dose administered). Three (3) additional subjects will be entered at the next lowest dose level if only 3 subjects were treated previously at that dose.
<1 out of 6 at highest dose level below the maximally administered dose	This is generally the recommended maximally tolerated dose.

The MTD will be defined as the highest safely tolerated dose where at most one patient in six experiences DLT during DLT observation period. The DLT observation period is defined as below.

Dose Level	DLT observation period
1	From the first dose of Daratumumab till 7 days post 3 rd dose
2/3	From the first dose of Daratumumab till at least 4 weeks post DLI

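### The 3-6 Phase I patients carried into the Phase II analysis is a one-ladder count; two donor ladders that each reach an MTD supply 6-12, and the plan does not say whether they sit inside the 25

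*Combined protocol and SAP*

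**What the plan says.** Section 16 applies the 3+3 rules within each donor cohort: "The dose escalation process for related sibling donor and unrelated donor will be conducted concurrently, but separately". The synopsis adds: "The MTD for the DLI may be different for related and unrelated donors". For Phase II, Section 16 says "we will combine these 2 cohorts together in phase II stage", with each cohort treated at its own MTD.

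The Phase II test has a 10% null response rate, a 30% alternative, alpha 0.05, power 0.80, 25 patients, and rejection at 6 or more responders. The carry-over sentence follows directly: "We would include 3-6 patients from" / "phase I who are treated at MTD in phase II analysis" (it runs across a page break). The next sentence allows for 10% not evaluable for efficacy and gives a Phase II enrolment of 25.

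The Phase I sizes in Section 16 (3 to 18 treated, 4 to 20 accrued) are for one ladder. Section 7.2 says so, and doubles the 4-20 to 8-40 for two cohorts. Nothing in the document doubles the 3-6. The synopsis and Section 7.1 also list a third, haploidentical, ladder, which Section 16 does not mention.

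**The concern.** The carry-over figure comes immediately after the statement that two separately escalated cohorts are combined, so it reads as a total. It matches the yield of one ladder only.

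Two things depend on it. One is how much of the primary Phase II result comes from patients already observed in Phase I. The other is the number analysed, and therefore whether the single cut-off of 6 responders still controls the type 1 error at the stated level. The plan fixes the cut-off for 25 patients. It does not say whether carried-over patients are part of that 25 or are added to it.

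**Working it through.** **Patients at the MTD in one ladder (Section 16 rules, three levels)**

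- The definition is "The MTD will be defined as the highest safely tolerated dose where at most one patient in six experiences DLT during DLT observation period". When escalation stops, three "additional subjects will be entered at the next lowest dose level if only 3 subjects were treated previously at that dose".
- MTD at level 1 or 2: the level above was too toxic, so the lower level has been filled to 6. Count: 6.
- MTD at level 3: either 0 of 3 with DLT and no expansion (count 3), or 1 of 3 then 0 of 3 (count 6).
- No MTD (level 1 too toxic): count 0.

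A ladder that reaches an MTD therefore gives 3 or 6. This reproduces the plan's 3-6.

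**Totals**

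- Two ladders, both with an MTD: 3+3 = 6, 3+6 = 9, 6+6 = 12, so 6-12.
- Two ladders, if the one-in-six definition also requires six patients at a top level cleared at 0 of 3: exactly 12.
- Only one of two ladders finds an MTD: 3-6.
- Three ladders including haploidentical, all with an MTD: 9-18.

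**The plan's Phase II size**

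Alpha = P(X ≥ 6 | n = 25, p = 0.10) = 0.0334. Power = P(X ≥ 6 | n = 25, p = 0.30) = 0.8065. The stated design reproduces, as a one-sided exact test.

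Enrolment: 25/0.9 = 27.8, rounded up to 28. The plan enrols 25, and 28 − 3 = 25, so the stated enrolment fits a carry-over of 3. This is an inference; the plan does not show the step.

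**Case A: carried-over patients count inside the 25 evaluable**

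- New patients needed: 28 − 6 = 22, 28 − 9 = 19, 28 − 12 = 16.
- Share of the 25, if every carried-over patient is evaluable: 6/25 = 24% to 12/25 = 48%.
- The cut-off of 6 remains correct.

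**Case B: 25 new patients are enrolled in addition**

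Evaluable number taken as 90% of the total; alpha is P(X ≥ 6 | n, 0.10).

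| Carried over | Total | 90% evaluable | n used | Alpha at cut-off 6 |
|---|---|---|---|---|
| 3 | 28 | 25.2 | 25 | 0.033 |
| 6 | 31 | 27.9 | 28 | 0.055 |
| 9 | 34 | 30.6 | 31 | 0.083 |
| 12 | 37 | 33.3 | 33 | 0.106 |

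If all 37 were evaluable, alpha would be 0.160. In Case B the carried-over share is 6/31 = 19% to 12/37 = 32% of the total.

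**Smallest cut-off with exact alpha at or below 0.05**

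- n = 25-27: 6 responders (alpha 0.033 to 0.047).
- n = 28-34: 7 responders (alpha 0.018 to 0.048; power 0.780 at n = 28, 0.812 at n = 29).
- n = 35-37: 8 responders (alpha 0.020 to 0.027).

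**The case against.** The best defence is that 3-6 was meant per cohort. The other Phase I counts in Section 16 are also one-ladder figures without a label, and Section 7.2 shows that they are per cohort. That is possible, and on that reading the 3-6 is correct. But the sentence does not say it and comes after the cohorts have been combined. The total and its place relative to the 25 would still need stating.

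A second defence is that a total of 3-6 arises if only one ladder finds an MTD. That is true, but the plan pools two cohorts each at its own MTD and makes no such condition. In the same spirit, 6-12 is not a guaranteed count. An MTD at level 1 involves no DLI, and Section 8.1 admits never-transplanted patients at that level. Whether they fit a Phase II endpoint of response to the combination in post-transplant relapse is left open.

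A reader might go further and infer any of three things that the documents do not support:

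- *That the number of new patients is also wrong by a factor of two.* The plan states 25 to enrol. With the 10% allowance and carry-over inside the 25, the need is 16-22, which is not half.
- *That nearly half of the primary result will be known before Phase II opens.* The 48% needs six patients at the MTD in both ladders, all evaluable, and all inside a fixed 25. The plan does not settle the last condition, and in Case B the share is 19-32%.
- *That pooling Phase I patients is itself an error.* It is openly pre-specified.

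**Conclusion.** The point holds as an under-specified carry-over with a consequence for error control. The 3-6 is right for one ladder. For the two ladders of Section 16 the total is 6-12, provided that each reaches an MTD.

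If carried-over patients are inside the 25, the test is unaffected, but new enrolment should be 16-22 and carry-over may be as much as 24-48% of the analysis set. If 25 are enrolled on top, exact one-sided alpha at the fixed cut-off is 0.055 to 0.106 for 28-33 evaluable. The low end is marginal: at 27 evaluable, alpha is 0.047.

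These figures assume that the 10% loss applies equally to carried-over and new patients, and that the test is one-sided, as the decision rule implies. They count only the two cohorts of Section 16; adding the haploidentical ladder would widen the gap.

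**What to change.** Amend Section 16, with matching text in Section 7.2, to:

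1. State the carry-over as 3-6 per donor cohort and 6-12 in total for two cohorts, fewer if a cohort finds no MTD.
2. Say which donor cohorts are pooled in Phase II, reconciling Section 16 with the haploidentical ladder in the synopsis and Section 7.1. Also reconcile the one-in-six MTD definition with the escalation table, which is silent on a top level cleared at 0 of 3.
3. Say that carried-over patients count within the 25 evaluable, and give new enrolment as 28 minus the carry-over (22, 19 or 16 for 6, 9 or 12).
4. Set the cut-off by the actual evaluable number: 6 responders at 25-27, 7 at 28-34, 8 at 35-37.

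The cost is one revised paragraph and a short cut-off table, with no extra patients. If the evaluable number lands at 28, the cut-off of 7 gives power of 0.78, just below the planned 0.80. Reporting ORR separately for carried-over and new patients beside the pooled estimate would be a useful descriptive addition, but is optional.
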